- In 2009, Galárraga used intraoperative botulinum toxin on 5 patients all younger than 6 months of age undergoing a primary cheiloplasty. The study showed the botulinum toxin injections to be safe without any complications observed. An EMG proven decrease in muscle activity around the repair site was also seen as predicted.
- Studies in adult patients have shown improved cosmetic outcomes for facial wounds when utilizing botulinum toxin. They have also established use of the toxin as safe in the face. Ziade et al. in 2013 showed injections of botulinum toxin type A within 72 hours postoperatively around facial wound repairs had better scar results at 1 year follow up as analyzed by 6 expert specialists. Wilson in 2006, showed utilization of botulinum toxin in revision facial scar surgery had 90 % of patients with a highly satisfactory outcome.

Objectives

Improve cheiloplasty outcomes with the use of intraoperative injection of botulinum toxin to clefted lip.

Study Design

- Randomized double blinded controlled trial of pediatric patients who require a primary unilateral cleft lip repair younger than 6 months of age. Utilization of botulinum toxin intraoperatively at targeted locations of the cleft lip. Surgeon, parents and expert panel of surgeons used at the completion study will all be blinded to which patients received the experimental injection.
- Control subjects will receive injections of normal saline at identical sites of the cleft lip as experimental subjects.
- 20 patients in each group will be enrolled.
- Patients will be evaluated preoperatively, postoperatively at 1 week, 1 month, 3 months, 6 months and 12 months of follow up.
- **Inclusion criteria:** Unilateral cleft lip with or without cleft palate, less than 6 months of age
- **Exclusion criteria:** Bilateral cleft lip, older than 6 months of age
- Primary endpoint: Blinded assessment of wound cosmesis by plastic surgeons and parents using scar assessment scale. At completion of follow up use of aesthetic grading criteria of videography images as described by Reddy et al. in 2008. These criteria include: Matching accuracy of white roll and vermillion border, scar appearance, Cupid's bow form, length of lip, nostril symmetry, alar dome form, and alar base position

Study Population

- Pediatric patients with complete unilateral cleft lip and palate less than 6 months of age undergoing cleft lip repair.

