- All patients who will be planned for a primary cleft lip repair will be offered to be enrolled in the study. Parents may choose to decline and undergo repair without enrollment in the study.
- Patients will be recruited as they would present otherwise to the University of Texas Pediatric Plastic Surgery Clinic to be evaluated for repair of cleft lip.

Study Procedures

- Patient will receive intraoperative botulinum toxin injections in the upper labial musculature prior to the operative repair being started.
- 4 injection sites will be used two superior and inferiorly in the cleft lip, 1 unit of botulinum toxin per injection site to be used. This is considered low dose in the pediatric population. Depending on the patient's weight it will be approximately 1 unit/kg.
- This dosing was chosen as it has been proven safe without any complications in prior pediatric botulinum toxin studies.
- This dosage has also been shown to adequately elicit muscle paresis in the head and neck.
- Patients will have videography performed preoperatively as well at scheduled post-operative visits.
- Parents will complete a Modified Vancouver Scar Scale at selective post-operative visits
- The Vancouver scar scale is a widely used validated scar scale for adults, however given our study it was modified appropriately for pediatric populations. There is no validated scar scale for pediatric patients.
- At the completion of the 1 year follow up period, videography will be sent to an expert panel of select plastic surgeons that will also use the Modified Vancouver Scar Scale to assess scar outcomes in both the control and experimental groups. This panel will be blinded to which patients received botulinum toxin and which received the control injection.
- Videography at the completion of the study will also be assessed for the following measures: Matching accuracy of white roll and vermillion border, scar appearance, Cupid's bow form, length of lip, nostril symmetry, alar dome form, and alar base position. Study personnel will be blinded to which patients received the experimental injection.
- No invasive procedures or postoperative monitoring will be employed unless deemed medically necessary.

Block Randomization

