- Oleszek et al. in 2005 performed botulinum toxin injections for patients aged 6-18 months with congenital torticollis. 29.7 units of botulinum toxin were used on average for each patient. Only 2 patients had transient neck weakness with mild dysphagia that resolved without intervention. They showed that even at higher doses botulinum toxin was safe to use in the head and neck.
- Of note our study will only use a low dose of 4 units of botulinum toxin total and will approximately be 1 unit/kg dosing depending on the weight of our study patient. This dosage is less than most pediatric botulinum toxin injection studies to date and therefore should be a safe dosage.
- As noted above a large number of studies have shown botulinum toxin to be safe at both low and high doses at a variety of anatomic locations including the head and neck.

Safety Monitoring

The PI, co-investigator and mentor will review any reported adverse events monthly.

- Patients feeding capabilities, respiratory status, neuromuscular function and overall health will be evaluated on each scheduled follow up visit.

Statistics

- Using the Modified Vancouver Scar Scale we hypothesize the average score for controls to be 7 out of 11. For experimental patients we expect an average score of 10 out of 11. Given a 90% confidence interval and standard deviation of 2.5 the necessary sample size would be 15 subjects per group using a 2 sided test.
- Therefore 20 patients will be the goal group size for each arm of the study; botulinum toxin injection group versus control group.
- The study will be terminated if any subjects display significant adverse side effects that are potentially life threatening including feeding, cardiovascular or respiratory complications.
- Study subjects to be used will be all patients who will undergo a primary cleft lip repair that agree to participation in the study and subsequent randomization.

Ethics

- Prior to initiating the study University of Texas Health Science Center at Houston Institutional Review Board will need to grant approval for the study.
- Consent will be obtained in person at the time of the pre-operative visit in the University of Texas Pediatric Plastic Surgery clinic. This consent will be in addition to the consent obtained for the surgical procedure. The known risks and adverse effects of botulinum toxin will be fully disclosed to parents prior to obtaining consent for the study.

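### The sample-size sentence gives a 90% confidence level and no power, so the trial's only error level is ambiguous and 15 per group cannot be checked

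*Combined protocol and SAP*

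**What the plan says.** All sizing information is in the Statistics section of the combined protocol and SAP.

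- Control mean: "Using the Modified Vancouver Scar Scale we hypothesize the average score for controls to be 7 out of 11".
- Experimental mean: "For experimental patients we expect an average score of 10 out of 11".
- Level, spread and result: "Given a 90% confidence interval and standard deviation of 2.5 the necessary sample size would be 15 subjects per group using a 2 sided test".
- Target: "Therefore 20 patients will be the goal group size for each arm of the study". The Study Design section repeats this as "20 patients in each group will be enrolled".

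Neither that section nor any other states a power, a significance level for the analysis, a named test or a dropout rate.

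The sizing also does not say whose scores, or which visit, it refers to. Study Design gives the endpoint as "Primary endpoint: Blinded assessment of wound cosmesis by plastic surgeons and parents using scar assessment scale". Under Study Procedures two groups score the same scale: "Parents will complete a Modified Vancouver Scar Scale at selective post-operative visits", and, once the 1-year follow-up is complete, "an expert panel of select plastic surgeons that will also use the Modified Vancouver Scar Scale".

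**The concern.** A two-group sample size needs a significance level and a power. The sentence supplies one percentage, calls it a confidence level, and leaves the power out. Taken at its word, it sets a two-sided alpha of 0.10, and at that alpha neither 80% nor 90% power leads to 15 per group. Either the label is not what was meant, or an unstated input produced the 15.

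This matters beyond the sizing because 90% is the only error level in the plan. An analyst looking for a threshold has nothing else to apply, and nothing prevents the level from being settled after the data are seen. Carried into the analysis, it gives a single comparison a 10% two-sided false-positive rate. The risk is higher if parent and panel scores are both tested and either may count as success. The plan neither says so nor rules it out.

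**Working it through.** **Inputs (Statistics section).** Means 7 and 10, so the difference is 3. SD 2.5, taken as common to both arms. Two-sided test, equal groups. Standardised difference d = 3/2.5 = 1.2. Power is not given, so the values below are assumptions.

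**Formula.** Normal approximation: n per group = 2(z₁₋α/₂ + z_power)²/d², with 2/d² = 2/1.44 = 1.389. The t-test column uses the noncentral t distribution.

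**Reproducing 15.** The stated inputs alone do not fix n. The closest match by the usual formula, rounded up, is alpha 0.05 with 90% power: 1.389 × (1.960 + 1.282)² = 14.59, giving 15.

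| Two-sided alpha | Power | Normal | t-test |
|---|---|---|---|
| 0.10 | 80% | 8.59 → 9 | 9.34 → 10 |
| 0.10 | 90% | 11.89 → 12 | 12.63 → 13 |
| 0.10 | 95% | 15.03 → 16 | 15.76 → 16 |
| 0.05 | 80% | 10.90 → 11 | 11.94 → 12 |
| 0.05 | 90% | 14.59 → 15 | 15.62 → 16 |

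**A precision reading.** If a 90% CI for the difference with half-width 1.5 was the target, n = 2 × (1.645 × 2.5/1.5)² = 15.03. The documents state no target width.

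**Power by t-test, normal scores.**

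| n per group | alpha 0.05 | alpha 0.10 |
|---|---|---|
| 15 | 88.7% | 94.1% |
| 16 | 90.7% | 95.3% |
| 20 | 95.9% | 98.1% |

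**Effect on the threshold at 20 per arm.** The smallest significant observed difference is t₁₋α/₂,₃₈ × 2.5 × √(2/20).

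- alpha 0.05: 2.024 × 0.791 = 1.60 points
- alpha 0.10: 1.686 × 0.791 = 1.33 points

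An observed difference between these two values is positive at one level and not at the other.

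**Two rater groups, either positive (illustration).** For two independent tests the false-positive rate is 1 − (1 − α)²: 9.75% at a 5% level and 19.0% at a 10% level. At an assumed correlation of 0.9 these become 7.0% and 13.6%. They describe two tests only and do not bound the whole plan, since parents score at more than one visit and the primary-endpoint bullet also lists aesthetic grading criteria.

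**Normality.** A normal distribution with mean 10 and SD 2.5 puts 1 − Φ((11 − 10)/2.5) = 34% of scores above the maximum of 11. The powers above are therefore nominal.

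**The case against.** The strongest reply is that nothing has been shown to be wrong. The match to alpha 0.05 with 90% power depends on one convention, the normal formula rounded up. By t-test that reading and alpha 0.10 with 95% power both give 16, and rounded to the nearest integer both give 15. The precision reading uses the words as written and is just as close. An unstated loss allowance would also work: 12 per group (alpha 0.10, 90% power) divided by 0.8 is 15. This stands. A reader might infer that the sponsor made an arithmetic error, or certainly wrote the power down as a confidence level. The documents support neither, because they give no power, target width or allowance against which to decide.

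A second reply is that the sentence only concerns sizing, so the 10% false-positive rate is hypothetical. That is right as far as it goes: no passage sets an analysis level or an either-may-win rule. But no other level exists in the plan, so the gap has to be closed somewhere.

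A third reply is that no passage mentions 0.05, so making it the default replaces the sponsor's wording. That is also fair. The 5% level is a recommendation, and a declared 10% level with its matching power would remove the ambiguity too.

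**Conclusion.** The concern holds as an ambiguity. The level is unclear, the power is unstated, and 15 per group does not follow from a literal 90% confidence level at 80% or 90% power. A mislabelled power is a plausible explanation but remains an inference.

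A reader might also conclude that the trial is too small. It is not, on these assumptions. The alpha and power readings that give about 15 call for at most 16 per group, and 20 are planned. At 20 per arm, t-test power is 95.9% at alpha 0.05 and 98.1% at alpha 0.10.

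The consequence lies in how the primary result is judged: a 5% or a 10% two-sided error rate for one comparison, and a positive or negative result for observed differences of about 1.33 to 1.60 points. These figures assume a 3-point difference for the powers, a common SD of 2.5, approximately normal scores and all 20 per arm evaluable. Normality is doubtful with an expected mean so close to the maximum. The loss of power from that cannot be quantified without the scale's structure and score distribution, so no adjusted range is offered.

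**What to change.** Replace the sizing sentence in the Statistics section with:

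> Two-sided alpha 0.05, difference 3, SD 2.5: 15 per group gives about 89% power by t-test (16 gives at least 90%); the planned 20 per group gives about 96% if all are evaluable, assuming approximately normal scores with equal SD.

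Add a caveat, without a power range, that a mean of 10 with SD 2.5 on a scale with maximum 11 makes normality doubtful.

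Name one Modified Vancouver Scar Scale comparison as primary (one rater group, one time point, one test), tested at two-sided 0.05 and reported with a 95% CI. Treat the other rater group's scores as supportive.

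If a 10% level was intended, say so and state the matching power: about 94% at 15 and 98% at 20 per group by t-test, with the same caveat.

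**Cost.** A few sentences and no extra patients. Compared with a 10% level at 20 per arm, the 5% level gives up about 2 points of power if the 3-point difference holds (95.9% v 98.1%). It gives up about 6 points at an assumed 2.5-point difference (86.9% v 92.8%) and about 11 at an assumed 2-point difference (69.3% v 79.9%). Naming one rater group as primary also rules out a claim based on the other group alone.

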Block randomization will be used for this study. The size of the blocks will not be fixed to ensure surgeons are truly blinded along with each arm of the study having the same number of patients. Therefore each group may have block sizes of 3, 5, 2, 6 and 4 to allow for a total of 20 patients. Both the ordering of blocks and their respective size will be blinded to eliminate any selection bias.

Drug Administration and Accountability

[name] MD, [name], MD and [name] will be responsible for botulinum toxin accountability. The toxin will be stored with the operating room pharmacy. As the study will be a randomized controlled trial, for those patients set to receive botulinum toxin, the medication will be requested from the OR pharmacy on the day of surgery. Prior to surgery it will be ensured the OR pharmacy has the toxin available. The toxin will be mixed as prescribed and 1 unit injections at 4 distinct sites will be used for a total of 4 units administered.

The pediatric plastic surgery research nurse will be responsible for notifying the operating room circulator whether that day's block of patients will be receiving the experimental versus the control injection.

Study patients will be attempted to be scheduled on the same OR days to maximize utilization of each botulinum toxin vial as they have a limited shelf life once mixed. Once the vial has been utilized it will be dispensed appropriately. The vials in the OR pharmacy will be stored in a standard cooled refrigerator as recommended by the manufacturer.

Possible Risks to Subjects

- Botulinum toxin safety has been well established. The FDA endorses that botulinum toxin use in a dermatologic fashion have no reported adverse side effects at the recommended doses. Studies which have utilized botulinum toxin in patients younger than 6 months of age have not reported significant adverse effects.
- Transient fatigue lasting no longer than 96 hours has been noted in a study by Pascual and Pascual in 2008 in one patient out of 74.
- The likelihood of risks are low and most studies have shown no side effects while few studies have noted transient fatigue in less than 5% of patients.
- Given that botulinum toxin takes 72 hours minimum to take effect there will be no change in the surgical procedure. Therefore there is no significant change in risk of the surgery itself.

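### The injection appears to be assigned to whole OR-day blocks, about five per arm, but the sample size treats infants as independently randomised and no block-level analysis is planned.

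*Combined protocol and SAP*

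**What the plan says.** Three statements describe the allocation.

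- Block Randomization: "each group may have block sizes of 3, 5, 2, 6 and 4 to allow for a total of 20 patients". The sizes add to 20 within one group, so each block belongs to one arm.
- Drug Administration and Accountability: the research nurse tells the operating room circulator "whether that day's block of patients will be receiving the experimental versus the control injection". That is one assignment per block.
- The same section gives the motive: "Study patients will be attempted to be scheduled on the same OR days to maximize utilization of each botulinum toxin vial".

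The Statistics section holds the only calculation. It says "we hypothesize the average score for controls to be 7 out of 11" and "For experimental patients we expect an average score of 10 out of 11". It continues "Given a 90% confidence interval and standard deviation of 2.5", and concludes that "the necessary sample size would be 15 subjects per group using a 2 sided test". The goal is then set at 20 per arm. The documents mention no block or day effect, ICC or design effect. Beyond the sample-size sentence, they name no test or model.

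**The concern.** When a whole block receives one injection, the block is the randomised unit. Infants in a block may share an operating day and, in the toxin arm, a reconstituted vial. Anything that differs between days and affects the scar then moves a whole block within one arm. With about five blocks per arm, such differences need not average out.

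An analysis that counts infants as independent would take this variation for extra information. It would reject a true null hypothesis too often and give too narrow an interval, so a positive result could partly reflect differences between days. The stated 15 per group would not deliver the precision that it implies. This holds however well blinding works, because blinding changes neither the correlation nor the number of randomised units.

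**Working it through.** **Inputs from the documents.** Means 7 and 10 (difference 3), SD 2.5, two-sided test, 15 per group, goal of 20 per arm (Statistics). Blocks of 3, 5, 2, 6 and 4 per arm (Block Randomization).

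**Assumption.** The ICC is not given. I use 0 to 0.20, the same in both arms.

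**1. The plan's 15.** With the formula for two independent means,

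n = 2 × [SD × (z for alpha + z for power) / difference]²

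- Two-sided 5%, 90% power: 2 × [2.5 × (1.960 + 1.282) / 3]² = 14.59, rounded up to 15. This matches.
- Two-sided 10%, 90% power: 12. This does not match.

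The plan's "Given a 90% confidence interval" fixes neither alpha nor power clearly, so I show both 5% and 10% below. Either way, the formula has no term for blocks.

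**2. Effect of the blocks on the variance.** The sum of squared sizes is 9 + 25 + 4 + 36 + 16 = 90, and 90/20 = 4.5. The design effect is 1 + (4.5 − 1) × ICC = 1 + 3.5 × ICC.

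- ICC 0.05: 1.175, so 20 per arm is worth 20/1.175 = 17.0 independent infants.
- ICC 0.10: 1.35, so 14.8.
- ICC 0.20: 1.70, so 11.8.

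**3. False-positive rate of an infant-level t test.** Simulated with the plan's block sizes, 20 per arm, 100,000 trials per ICC:

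| ICC | Nominal 5% | Nominal 10% |
|---|---|---|
| 0 | 5% | 10% |
| 0.02 | 6% | 11% |
| 0.05 | 7% | 13% |
| 0.10 | 9% | 16% |
| 0.20 | 14% | 21% |

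If blocks span several days and infants are alike only within days of two, the nominal 5% test runs at about 6%, 6% and 7% at ICC 0.05, 0.10 and 0.20.

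**4. Power of a block-level analysis at 20 per arm.** Ten blocks less two arms leaves 8 df. The average of 1/size is (1/3 + 1/5 + 1/2 + 1/6 + 1/4)/5 = 0.29. The standard error of the difference in block means is therefore

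√{2 × (2.5²/5) × [ICC + (1 − ICC) × 0.29]}

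At ICC 0.10 this is √(2.5 × 0.361) = 0.95, so the noncentrality is 3/0.95 = 3.16. From the noncentral t on 8 df:

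| ICC | Power, two-sided 5% | Power, two-sided 10% |
|---|---|---|
| 0 | 87% | 94% |
| 0.05 | 83% | 92% |
| 0.10 | 79% | 89% |
| 0.20 | 72% | 84% |

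For comparison, 20 independent infants per arm would give 96% at 5% and 98% at 10%.

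**5. Why 15 × design effect is not the answer.** It gives 15 × 1.175 = 17.6 and 15 × 1.35 = 20.25, or about 18 and 20 per arm at ICC 0.05 and 0.10. That corrects the variance but ignores the few df. With block-level df and an average block of 4, 90% power at two-sided 5% needs about 24 per arm (6 blocks) at ICC 0.05 and 28 (7 blocks) at ICC 0.10.

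**The case against.** **No infant-level test is specified.** A reader might infer that the plan prescribes one. It does not; it names no test at all. The error rates above belong to the analysis that the sample-size sentence implies. What stands is that the calculation has no block term and that the unit of analysis is left open.

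**The link between block and day is not firm.** Block sizes are only possible ones, and shared operating days are only attempted. Elsewhere the protocol speaks of individual patients set to receive toxin, and of subjects agreeing to randomisation. Nothing says that a block of 5 or 6 is completed in one day, and smaller day groups shrink the inflation, as step 3 shows. Even so, the nurse's instruction is given for a block, and odd sizes such as 3 and 5 cannot be balanced 1:1 within a block.

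**The ICC may be small.** The trial has one site, toxin is prepared in the same way for each patient, and the camera is calibrated before each session. No text says that teams differ between days, and vial sharing affects only the toxin arm. This is fair: at ICC 0 the infant-level test is not inflated. The direction is certain only for an ICC above 0.

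**The goal is 20, not 15.** That margin absorbs the design effect alone up to an ICC of about 0.10, but not the loss of df. Nor do the documents support the stronger inference that 20 per arm is inadequate. They state no power target, and at the 10% level that the plan's wording literally suggests, block-means power is 84% to 94%.

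**Conclusion.** The concern holds as a mismatch between the allocation, as the protocol most naturally reads, and the only statistical calculation. The figure of 15 per group is correct arithmetic for independent infants, but the described allocation does not supply independent infants.

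An infant-level comparison would exceed its nominal 5% by little at an ICC of 0.02 and by a factor of nearly three at 0.20. These sizes rest on three assumptions: an ICC that the documents do not give, single-arm blocks of the listed sizes, and an infant-level analysis that the plan implies but does not state. The finding does not show that the trial is too small or that a positive result would be false. It shows that the unit of analysis must be written down and the stated size replaced.

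**What to change.** First settle, in Block Randomization and in Drug Administration and Accountability, whether the block or the infant is randomised.

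- **If OR-day blocks keep a single arm:** state in Statistics that the comparison uses the randomised block as its unit. Use either block means on 8 df, or a mixed model with a random block effect and small-sample df. Replace the claim that 15 per group suffices with the power of the planned 20 per arm under that analysis, at a named two-sided level and over a stated ICC range, as in step 4. Do not restate the size as 15 × design effect. If the number or sizes of the blocks change in practice, the df and power change with them.
- **If infants are randomised individually:** say so in both sections. No correction for blocks is then needed.

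The change is to wording only and needs no extra infants. With single-arm blocks, the cost is a wider interval and a lower stated power, for example 79% against 96% at two-sided 5% and ICC 0.10.
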